**5.2.7 Re-Screened and Re-Randomized Subjects**

In the event a subject is re-screened, then the data from the last screening visit, and latest laboratory assessment are used for the screening data.

In the event a subject is re-randomized, the subject will not be analyzed as part of the mITT population for the efficacy analyses. For safety, all AEs that occurred after the date of randomization for the treated subjects will be considered on-study. If such a subject is treated at least once with BHV-3000 (rimegepant), then their treatment assignment is BHV-3000 (rimegepant) for all treated subject numbers pertaining to the same subject.

### **5.2.8 Missing and Partial Dates**

For efficacy analyses, partial or missing dates will not be imputed. The relative study days, where determined, will be calculated for full dates only.

For rescue medication, if the time of rescue medication is missing, then all endpoints on or after the date of rescue medication will be imputed as failures.

For missing and/or partial dates regarding concomitant/prior medications, a conservative approach will be taken. The medication will be assumed to be concomitant if it cannot be definitively shown that the medication was not taken after the period beginning 14 days prior to the taking of study medication.

If the start date of an AE is partially or completely missing, then the date will be compared as far as possible with the date of the randomization. The AE will be assumed to be on-study if it cannot be definitively shown that the AE did not occur or worsen during the post-randomization period (worst case approach).

The following general rules will be used:

- If the start day is missing, but the start month and year are complete, an AE will only be excluded as being on-study if the start month/year is before the month/year of randomization or if the stop date is before randomization.
- If the start day and month are missing, but the start year is complete, an AE will only be excluded as being on-study if start year is before the year of randomization or if the stop date is before randomization.
- If the start date is completely missing, an AE will be considered on-study unless the stop date is before randomization.

### **5.2.9 Visit Windows**

Windows for the timeframe around efficacy measurements (15, 30, 45, 60, 90 minutes, 2, 3, 4, 6, 8, 24, and 48 hours) will be automated and captured in the eDiary. Refer to [Table 6](#) for details on the evaluation intervals and [Appendix 1](#) for details on the schedule of assessments.

**Table 6: Evaluation Intervals for Efficacy Analysis**

Evaluation	Protocol-Specified Interval	Analysis-Specified Interval
Screening Phase		
Screening	Day -28 to Day -3	Day -40 to Day -3
Acute (Randomization) Phase		
Baseline (Randomization)	Day 1	Day -2 to 1
Onset of Migraine	Day 1 to 45	Day 1 to 45
15, 30, 45, 60, 90 minutes post-dose	Time of Dose + 15, 30, 45, 60, and 90 minutes	Time of Dose + 15, 30, 45, 60, and 90 minutes (as captured in eDiary)
2 hours post-dose	Time of Dose + 2 hours	Time of Dose + 2 hours (as captured in eDiary)
8 hours post-dose	Time of Dose + 8 hours	Time of Dose + 8 hours (as captured in eDiary)
24 hours post-dose	Time of Dose + 24 hours	Time of Dose + 24 hours (as captured in eDiary)
48 hours post-dose	Time of Dose + 48 hours	Time of Dose + 48 hours (as captured in eDiary)
End of Treatment Visit	Time of Dose + 7 days	Time of Dose + 2 to 21 days

### 5.3 Planned Analyses

The analyses planned for endpoints that use data from this study only will be conducted after the last subject completes their End of Treatment Visit or discontinues from the study, and the database has been locked.

A meta-analysis of the durability endpoints will be conducted after the last subject in BHV3000-301 and BHV3000-302 completes their End of Treatment Visit or discontinues from the study, and both databases have been locked.

### 5.4 Subject Disposition

[figure not shown]
A summary of subject disposition will be tabulated for all subjects by treatment group and overall. The disposition table will support the creation of a consort diagram, similar to that shown in Figure 1. The categories in the table will include:

- Number of subjects screened
  - Number of screened subjects excluded from the study and reason for exclusion
- Number of subjects randomized
  - Number of subjects not treated, and the reasons for not being treated

- Number of subjects treated, and their status
  - Completed Study
  - Discontinued, and reasons for discontinuation
- Number of subjects in each analysis population
- Number of subjects who intend to continue on to the BHV-3000-201 study.

A by-subject listing of subject disposition information, including the reason for withdrawal, if applicable, will be presented.

**Figure 2: Consort Diagram**

## 5.5 Demographic and Baseline Characteristics

Demographic information, medical history, migraine history, cardiovascular risk factors, and prior/current triptan response will be summarized by treatment group and overall for the mITT population. A similar set of tables will be made for the treated population.

A separate set of demographic tabulations, including demographic information and migraine history, will be made for subjects enrolled but not randomized (overall only) and subjects randomized but not treated (by randomized treatment and overall).

Demographic and other baseline data will also be provided in by-subject data listings.

## 5.6 Missing Data Description

Descriptions and tabulations of missing data will only be concerned with the post-baseline time points required for computation of the primary and secondary endpoints. These include the time points measured from 2 hours through 48 hours post-dose (e.g.: 2, 3, 4, 6, 8, 24 and 48 hours). The other time points: 15, 30, 45, 60 and 90 minutes are only required for the exploratory endpoints. Also, some tabulations focus on the pain endpoint as that should be generally descriptive of the other efficacy endpoints.

The number and percentage of randomized subjects that were randomized but not treated will be tabulated by treatment group.

For the mITT population, the items below will be tabulated by treatment group and overall, and sub-tabulated by date of migraine onset relative to September 13, 2017 ( date  $\leq$  13-Sep-2017; date  $>$  13-Sep-2017; overall). Hence, there are three subcategories tabulated within each of two treatment groups and overall.

- Number and percentage of subjects with missing pain data at each time point from 2 through 48 hours post-dose. The categories in this tabulation are not mutually exclusive as subjects may have missing data at multiple time points.
- Number and percentage of subjects with: no missing pain data; 1 missing time point, 2 missing time points, 3 missing time points, 4 missing time points, 5 missing time points, 6 missing time points, or 7 missing time points. The categories in this tabulation are mutually exclusive.
- The number and percentage of subjects with missing data on the following endpoints measured at 2-hours post-dose: pain, MBS, photophobia, phonophobia, nausea, and functional disability.

In addition, the number and percentage of mITT subjects with missing pain data at 2 hours post-dose will be displayed by treatment group and overall within the categories of each of the following subgroups:

- Age: Categorized as < 40 or ≥ 40 years
- Race: white; black or African American; all other races combined (including Asian); Asian only
- Sex: Female or Male
- Aura for study migraine: Presence or Absence
- Headaches per Month: Categorized as < median or ≥ median
- Triptan Non-Responder: Yes/No
- Rescue medication taken at anytime during the study: Yes/No
- MBS at migraine onset: photophobia, phonophobia, nausea, and not reported

## **5.7 Efficacy Evaluation**

Unless otherwise noted, all efficacy analyses will be conducted using the mITT population as outlined below. All efficacy data will be included in listings by subject, study medication, and time point (as applicable). For efficacy analyses, baseline is considered as the assessment at the onset of the treated migraine. Subjects who were randomized twice will not be included in the efficacy evaluation.

### **5.7.1 Rescue Medication**

Subjects who take rescue medication as recorded on the CRF or any medication used for headaches as recorded anywhere on the CRF or eDiary will be considered as failures for any efficacy evaluations that are coincident or follow the administration of the rescue medication/other headache medication. If the time of rescue medication is missing, subjects will be considered as failures for any efficacy evaluations are on or after the date of administration of the rescue medication/other headache medication.

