5.4 Prohibited Concomitant Medication

The below medications are prohibited prior to randomization and during the course of this study or as specified.

1. St. John's Wort should not be taken 14 days prior to randomization and throughout the study.
2. Butterbur root or extracts should not be taken 14 days prior to randomization and throughout the study.
3. History of use of ergotamine medications on greater than/equal 10 days per month on a regular basis for greater than/equal 3 months
4. History of non-narcotic analgesic intake on greater than/equal 15 days per month for greater than/equal 3 months
5. Use of narcotic medication, such as barbiturates, heroin, opium in the form of morphine and codeine, oxycodone and hydrocodone for at least 2 days prior to randomization.
6. Use of acetaminophen or acetaminophen containing products at daily dosing levels greater than 1000mg/day for at least two days prior to randomization.
7. Use of marijuana is prohibited during the study.

Patients on prophylactic migraine medication are permitted to remain on therapy provided they have been on a stable dose for at least 3 months prior to study entry.

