5.4.1 Rescue Medications

After dosing with study medication, all other headache medication is prohibited during the 2 hours post dose. However, a patient who does not experience relief of their migraine headache at the end of two hours after dosing with study medication (and after the two hour assessments have been completed on the eDiary), will be permitted to use the following rescue medication: aspirin, ibuprofen, acetaminophen up to 1000mg/day (this includes Excedrin Migraine) naprosyn (or any other type of non-steroidal anti-inflammatory (NSAID)), antiemetics (e.g., metoclopramide or promethazine), or baclofen. These are the only medications allowed for rescue treatment after 2 hours post dose of study medication. However, if needed, after 48-hours of administering the one dose of study medication (and before coming in for the End of Treatment Visit) patients may take their prescribed standard of care medications for treatment of migraine (including triptans if not contraindicated, **provided all of the assessments have been completed on the eDiary**). Similarly, if the migraine is relieved by study medication at 2 hours after dosing but then recurs to a moderate or severe intensity level between two and forty-eight hours, the patient will be permitted to take the same rescue therapy as outlined above. In all circumstances, the patient will always continue to complete his or her eDiary for up to forty-eight hours after consuming the study medication. Use of concomitant medication after randomization, including rescue medication, will be recorded by the patient on a paper diary and reported to the site. The site will record medications that were taken within 14 days of dosing with study medication (or until the End of Treatment Visit).

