**RM=F: Rescue Medication = Failure.**

Subjects that take rescue medication before, or at, the time of the event of interest are classified as failures. If the time of rescue medication is missing, all events on or after the date of rescue medication are classified as failures.

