#### 5.7.3.2 *Freedom from MBS at 2 Hours Post-Dose*

Freedom from each subject's MBS is assessed using the number of mITT subjects who report that their MBS (reported at migraine onset) is absent at 2 hours post-dose. The symptoms that can be nominated as the MBS (phonophobia, photophobia or nausea) are measured using a binary scale (0=absent, 1=present).

Subjects who reported their MBS before taking IP, or who did not provide an MBS are considered failures in this analysis.

Tabulations will be presented as follows:

- The number and percentage of subjects reporting each of the migraine associated symptoms (phonophobia, photophobia or nausea) as most bothersome, subjects with a missing MBS, and subjects who reported their MBS after taking study medication.
- A cross tabulation of the historical MBS (reported at screening) as rows, and the MBS reported at the onset of the treated migraine as columns. This tabulation only includes subjects with both assessments. P-value from a chi-square test will be reported along with the values and confidence limits for both Asymmetric Lambda and Symmetric Lambda.

The estimand, difference in percentage of MBS free subjects (“risk difference”) between treatment groups, is evaluated by computing the common risk difference, using CMH weights (sample size weights), stratified by the use of prophylactic migraine medication (yes or no). The risk difference will be tested at a two-sided alpha level of 0.05. Missing data at 2 hours post-dose will be imputed as failure (NC=F). Also the use of rescue medication prior to providing data at the 2 hour assessment, taking IP prior to reporting the MBS, or failure to report a MBS are events that are imputed as treatment failures. If a stratum (prophylactic medication use: yes or no) has sparse data (less than 5 subjects) then the strata will be pooled.

The results to be presented for the primary analysis of MBS include those described in items (a) through (e) for the primary analysis of pain freedom (Section 5.7.3.1). In this case, the “risk” is now the probability of being MBS free at two-hours post-dose.

The primary analysis of MBS will be repeated for the subgroups described in Section 5.2.6.

Sensitivity analyses will be conducted as follows:

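### The SAP rescue rule counts any recorded headache medication and has no start time, so as written it fails subjects on both co-primaries for treating an unrelated earlier headache

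*SAP*

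**What the plan says.** The estimand rule in SAP 2.3 reads: "Subjects that take rescue medication before, or at, the time of the event of interest are classified as failures". It sets an upper time limit only and is confined to rescue medication. SAP Table 1 applies RM=F to both co-primaries. SAP Table 2 applies it to ten of the eleven secondary endpoints, the exception being the rescue endpoint itself.

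SAP 5.7.1 goes further. Besides rescue medication it names "any medication used for headaches as recorded anywhere on the CRF or eDiary will be considered as failures for any efficacy evaluations", and the evaluations concerned are "any efficacy evaluations that are coincident or follow the administration of the rescue medication/other headache medication". It gives no earliest time and no exception for prophylaxis.

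The endpoint sections are narrower. For freedom from the most bothersome symptom (MBS), SAP 5.7.3.2 names "the use of rescue medication prior to providing data at the 2 hour assessment". SAP 5.7.4.1 (photophobia, phonophobia, nausea) likewise speaks only of rescue medication.

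On data capture, Protocol 5.4.1 states: "The site will record medications that were taken within 14 days of dosing with study medication". SAP 5.2.8 treats medication as concomitant from 14 days before study drug. Protocol Table 1, footnote 3, has subjects record concomitant medication from randomisation onwards, and dosing may follow up to 45 days later.

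On prophylaxis, Protocol 5.4 states: "Patients on prophylactic migraine medication are permitted to remain on therapy provided they have been on a stable dose". Its use is the randomisation stratum and the stratum of the co-primary tests.

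**The concern.** A failure rule for rescue is meant to stop relief from another drug being credited to study drug. That needs an interval tied to the treated attack. Without a start point, a headache medication taken a week before the study attack is followed by the 2-hour assessment and so triggers failure, although it cannot explain relief of that attack.

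Acute medication taken for the study attack shortly before study drug is a harder case. Protocol 5.4 does not list NSAIDs or triptans as such among its prohibited medications, and the ban on other headache medication in Protocol 5.4.1 starts after dosing. SAP 5.7.1 may then be the only text that decides how such a subject is scored: a failure on the literal reading, possibly a success on a post-dose reading.

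At stake is the definition of success on both co-primaries and most of the fixed-sequence secondaries. The literal rule also pulls the estimated difference towards zero.

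**Working it through.** **1. The passages side by side**

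| Place | Medication that counts | Earliest time | Latest time |
|---|---|---|---|
| SAP 2.3, RM=F | rescue | none stated | event of interest |
| SAP 5.7.1 | rescue or any recorded headache medication | none stated | evaluation |
| SAP 5.7.3.2 | rescue | none stated | 2-hour data |
| SAP 5.7.4.1 | rescue | none stated | 2-hour data |

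The SAP's 14-day window (5.2.8) classifies medication as concomitant and does not limit 5.7.1. If the time of a medication is missing, every evaluation on or after its date fails. That also catches medication taken earlier on the dosing day.

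**2. The plan's own figures**

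Inputs: 550 treated per arm, two-sided alpha 0.05, 1:1 allocation (SAP 5.1, 5.2.5, 2.2); Phase 2b pain freedom 31.4% against 15.3% (Protocol 1.3.2.8).

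Power = Φ[(d − 1.96·SE0)/SE1], where SE0 = √[2p̄(1−p̄)/n] and SE1 = √{[p1(1−p1) + p2(1−p2)]/n}.

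Here d = 0.161, p̄ = 0.2335, SE0 = 0.0255 and SE1 = 0.0250. The argument is (0.161 − 0.0500)/0.0250 = 4.43, so power exceeds 99.9%. The stated figure of more than 95% is reproduced. It also holds at 540 per arm (0.9 × 600). The joint bound is 1 − 0.05 − 0.05 = 0.90, as stated.

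No Phase 2b MBS rates are given. As a proxy, the symptom with the lowest power is nausea, 67.4% against 51.2% (Protocol 1.4.2), which gives 99.98%.

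**3. Effect of the literal rule**

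Suppose a share f of each arm is failed whatever it reports. Each rate becomes (1−f)p and the difference (1−f)d. The documents do not give f, so the range is an assumption.

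| f | Pain freedom | Difference (points) | Power, pain freedom | Power, nausea proxy |
|---|---|---|---|---|
| 0 | 31.4 vs 15.3% | 16.1 | >99.9% | 99.98% |
| 10% | 28.3 vs 13.8% | 14.5 | >99.9% | 99.8% |
| 20% | 25.1 vs 12.2% | 12.9 | >99.9% | 99.1% |
| 30% | 22.0 vs 10.7% | 11.3 | 99.9% | 96.9% |

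Power falls below 95% at f of about 61% for pain freedom, 58% for the photophobia proxy (41.9% against 24.1%) and 35% for the nausea proxy.

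If the true pain-freedom effect were half that of Phase 2b (an assumption: 23.35% against 15.3%), power would be 92.3% at f = 0 and 84.1% at f = 20%.

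**4. Type I error**

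Under the null both arms have rate p, and equal forced failure leaves both at (1−f)p. Medication taken before the blinded dose should be balanced by randomisation, so there is no inflation.

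**The case against.** The strongest reply is that context already supplies a post-dose meaning. The section is headed as a rescue rule. Protocol 5.4.1 describes rescue as post-dose treatment ("These are the only medications allowed for rescue treatment after 2 hours post dose of study medication") and speaks of other headache medication in the same setting: "After dosing with study medication, all other headache medication is prohibited during the 2 hours post dose". The rescue endpoint in SAP 5.7.4.3 counts use after the dose. The literal reading also defeats itself: study drug is a headache medication whose intake is recorded in the eDiary, so every treated subject would fail.

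This shows that a fully literal application is not intended. It does not supply the missing start time. SAP 5.7.1 deliberately adds other headache medication to rescue, and nothing says whether acute medication taken for the study attack before study drug counts.

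Two stronger readings are tempting, and neither is supported.

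- **That the plan fails every prophylaxis user.** The wording makes no exception, and applied literally the prophylaxis-yes stratum would have no responders in either arm and a risk difference of zero. But SAP 5.7.3.1 plans a risk difference, p-value and interval within each stratum, and Appendix 1 lists prophylactic and rescue medications separately (16.2.11.3.2 and 16.2.11.3.3). The plan evidently expects responders there.
- **That attack frequency shows most subjects would be failed.** Entry requires 2 to 8 moderate or severe attacks a month. With Poisson attacks, the chance of another in the 14 days before dosing is 1 − exp(−m), with m = rate × 14/30: 61% to 98%. If the first qualifying attack after randomisation is the one treated with study drug, an earlier one must precede randomisation, and the chance is 1 − exp(−m)(1 + m): 24% to 89%. Both count attacks, not attacks that were treated and recorded, so neither estimates f.

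**Conclusion.** The point holds as a defect of wording in a confirmatory rule, of minor to moderate weight. SAP 5.7.1 is broader than the estimand and endpoint sections it serves and has no lower time limit. As written, it fails subjects at 2 hours for treating an unrelated earlier headache.

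The consequence is a pain-freedom difference diluted from 16.1 to between 14.5 and 11.3 points at an assumed f of 10 to 30%, together with a success rule left open to interpretation. Power on pain freedom stays at about 99.9% or more over that range, so the trial is not put at risk. These sizes rest on Phase 2b rates, equal f in both arms, and an f that the documents do not give.

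**What to change.** In SAP 2.3 (RM=F) and 5.7.1, with matching wording in 5.7.3.2 and 5.7.4.1, state:

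- RM=F counts acute headache medication, other than study drug, taken from the recorded onset of the treated migraine up to and including the assessment. This includes acute medication taken for that attack before study drug.
- Stable prophylactic migraine medication, and headache medication taken before that onset, do not trigger RM=F.
- The conservative rule for missing medication times stays as it is.

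Starting at onset rather than at study-drug intake is a choice. Run each co-primary once more with the interval starting at study-drug intake, to show whether it matters.

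The cost is a few sentences and one extra run per co-primary. Headache onset and dosing times are already in the eDiary, and rescue date and time are already listed (SAP 5.7.4.3). This is an analysis rule only; it changes nothing about which medications patients may take.

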### **5.7.2 MBS Recored After IP is Taken**

Subjects that record their MBS after taking the investigation product (IP) are considered failures for the analysis of MBS.

### **5.7.3 Primary Efficacy Endpoints**

In addition to the analyses described below, data regarding the co-primary efficacy endpoints, pain freedom and freedom from MBS at 2 hours post-dose, will be presented in a listing that includes treatment group, historical MBS, MBS at time of onset of study migraine, initial migraine severity, gender, presence or absence of aura, and use of prophylactic migraine medication.

### 5.7.3.1 Pain Freedom at 2 Hours Post-Dose

Pain freedom is assessed using the number of mITT subjects that report pain levels of “none” at 2 hours post-dose on a 4-point Likert scale (0=none, 1=mild, 2=moderate, 3=severe). The information from the 4-point scale is directly summarized as follows:

- A table showing descriptive statistics for the observed data, which includes the number and percentage of subjects reporting each of the 4 pain levels at 2 hours post-dose, and the percentage of subjects with missing data, for each treatment group. The table will include exact (Clopper-Pearson) 95% CIs for each percentage.
  - This table will be repeated for Asian subjects only.

The estimand for the primary analysis is the percentage of pain free subjects. In statistical terms, this percentage is arrived at by estimating the probability or the “risk” that a subject is pain free.

The population summary, the between group difference in the percentage of pain free subjects is assessed by computing the “risk difference” between treatment groups. This is evaluated by computing the common risk difference, using Cochran-Mantel-Haenszel (CMH) weights (sample size weights), stratified by the use of prophylactic migraine medication (yes or no). The risk difference is tested at a two-sided alpha level of 0.05. Missing data at 2 hours post-dose will be imputed as failures (NC=F). If a stratum (prophylactic medication use: yes or no) has sparse data (less than 5 subjects), then the strata will be pooled.

Results presented for the primary analysis include the following:

- The number and percentage of subjects who are pain free, and those not pain free, at 2 hours post-dose. These are presented by stratum and treatment group, with asymptotic standard errors (ASE), and 95% asymptotic CIs.
- Common risk difference with sample size, p-value, asymptotic standard error (ASE), and 95% asymptotic CIs.
- Risk difference within each strata with sample size, p-value, asymptotic standard error (ASE), and 95% asymptotic CIs.
- A plot of the risk differences within each strata, and common risk difference (similar to the risk difference plot produced by SAS Proc Freq).
- Common risk for each treatment with sample size, ASE, and 95% asymptotic CIs.

The primary analysis will be repeated for the subgroups described in Section 5.2.6.

Sensitivity analyses will be conducted as follows:

1. The primary analysis is repeated, once using the mITT subjects that had a qualifying migraine before the last relevant software fix was applied to the eDiaries (onset on or before 13-Sep-2017), and once for mITT subjects with migraine onset dates after the software fix was applied (onset after 13-Sep-2017).
2. The primary analysis is repeated, using the mITT population, with missing data at 2 hours post-dose imputed using Last Observation Carried Forward (LOCF). Baseline Observation Carried Forward (BOCF) is permitted.
3. The primary analysis is repeated using only data from complete cases (data present at baseline and 2 hours).
4. The primary analysis is executed using the mITT population, and multiple imputation (with 20 imputations;  $m=20$ ) methods to impute missing data at 2 hours post-dose using the copy from reference approach. The fully conditional specification (FCS) method is used with a generalized logit distribution. Covariates may include use of prophylactic medication (yes or no), sex, migraine intensity at onset (severe or other), migraines per month ( $<$  median,  $\geq$  median), date of migraine onset (on or before 13-Sep-2017 or after 13-Sep-2017), and the subject's MBS at time of study migraine onset (nausea, photophobia, or phonophobia).
5. A series of "what if" analyses are conducted that show what the analysis results would look like if the missing data in each treatment group were replaced with data from subjects having success rates that vary over the range of 0, 10, 20 and 30 percent. This analysis is presented in a 4x4 matrix, with the rows representing the success rates for the placebo group and the columns representing the success rates for the BHV-3000 group. For example, the "30,0" cell shows the hypothetical results when a responder rate of 30% replaces the missing placebo data, and a responder rate of 0% replaces the missing BHV-3000 data. Each cell in this table will show the common risk difference, asymptotic 95% CI and uncorrected p-value. The table will be accompanied by a forest plot that displays the 16 CIs.

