5.1 Number of Subjects

It is anticipated that 1415 patients will need to be screened in order to randomize approximately 1200 patients. If, however, the minimum number of treated subjects is reached first, the study may be closed. The subjects will be randomized in a 1:1 ratio to the rimegepant or placebo treatment groups. It is anticipated that enrollment will occur at approximately 50 sites in the United States over a period of approximately 3 months during this trial.

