9.4 Statistical Methods

9.4.1 Primary Endpoint(s)

BHV-3000 (rimegepant) is tested for superiority to placebo, at an $\alpha=0.05$ level, on both pain freedom at 2 hours post-dose and freedom the most bothersome symptom at 2 hours post-dose. Both endpoints are evaluated using Cochran-Mantel Haenszel tests. The test for pain is stratified by the use of prophylactic migraine medication (yes or no). The test for the most bothersome symptom is also stratified by the use of prophylactic migraine medication (yes or no). These tests are conducted using the mITT subjects, with missing data at two hours imputed to be failure (i.e., Non-Completers = Failure; NC=F). Sensitivity analyses are described in the Statistical Analysis Plan (SAP).

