1. The primary analysis is repeated, once using the mITT subjects that had a qualifying migraine before the last relevant software fix was applied to the eDiaries (onset on or before 13-Sep-2017), and once for mITT subjects with migraine onset dates after the software fix was applied (onset after 13-Sep-2017).
2. The primary analysis is repeated, using the mITT population, with missing data at 2 hours post-dose imputed using Last Observation Carried Forward (LOCF). Baseline Observation Carried forward is permitted.
3. The primary analysis is repeated, using only data from complete cases (data present at baseline and 2 hours).
4. The primary analysis is executed using the mITT analysis set, and multiple imputation (with 20 imputations;  $m=20$ ) methods to impute missing data at 2 hours post-dose using the copy from reference approach. The FCS method is used with a generalized logit distribution. Covariates may include use of prophylactic medication (yes or no), sex, migraine intensity at onset (severe or other), migraines per month ( $<$  median,  $\geq$  median), date of migraine onset (on or before 13-Sep-2017 or after 13-Sep-2017), and the subject’s MBS at time of study migraine onset (nausea, photophobia, or phonophobia).

5. A matrix of “what if” analyses, similar to that created for the co-primary endpoint of pain freedom, is created for freedom from the MBS.
6. The primary analysis will be repeated, using the mITT population, with the addition of a strata that reflects the subject’s self-reported MBS at the time of study migraine onset (nausea, phonophobia, or photophobia).

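### Onset pain severity, recorded before dosing, is a stratum in no analysis of either co-primary; adding it for pain freedom would buy a little precision, and MBS sensitivity analysis 6 needs a fourth level

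*SAP*

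**What the plan says.** SAP 5.7.3.1 estimates the pain-freedom difference with CMH weights, "stratified by the use of prophylactic migraine medication (yes or no"). It adds that "The risk difference is tested at a two-sided alpha level of 0.05". SAP 5.7.3.2 does the same for MBS freedom, "using CMH weights (sample size weights), stratified by the use of prophylactic migraine medication (yes or no"). Protocol 9.4.1 agrees: "The test for the most bothersome symptom is also stratified by the use of prophylactic migraine medication". SAP 5.2.4 gives the reason, which is that prophylaxis was the factor stratified at randomization.

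Protocol 4.3.2 has subjects enter pain intensity in the eDiary before they dose, and SAP 5.7 takes the onset assessment as the efficacy baseline. Onset severity then appears in two places only: the listing of co-primary data (SAP 5.7.3), and the optional imputation covariates of sensitivity analysis 4, as "migraine intensity at onset (severe or other"). It is not among the subgroups in SAP 5.2.6.

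MBS type was once a stratum for the MBS test. The protocol's summary of changes records its removal. The SAP keeps it as MBS sensitivity analysis 6, which repeats the primary analysis on the mITT population "with the addition of a strata that reflects" the MBS at onset, with nausea, phonophobia and photophobia as the levels.

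**The concern.** Stratifying on a baseline factor that predicts the outcome usually narrows the interval and removes chance imbalance in that factor. Onset severity is the baseline value of the scale on which pain freedom is scored. It is known for every mITT subject, because SAP 4.1 admits only those with a moderate or severe baseline attack, so it needs no missing-value category. What is at stake is some precision, not validity.

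Sensitivity analysis 6 raises a separate point. SAP 5.7.3.2 expects some subjects to have no MBS, or one recorded after dosing, and SAP Table 1 counts both as failures. A subject with no MBS fits none of the three levels, and a post-dose MBS is not a baseline value. If a programmer leaves such subjects out, the analysis changes the population as well as the strata, and it no longer shows the effect of stratifying alone.

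**Working it through.** **1. The plan's own power.** Inputs: two-sided alpha 0.05 (SAP 5.7.3.1); 1:1 allocation (Protocol 5.1); about 550 treated per arm (Protocol 9.2; 90% of 600 is 540); Phase 2b pain freedom 31.4% vs 15.3% (Protocol 1.4.2).

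Power = Φ{[Δ − 1.96·√(2p̄(1−p̄)/n)] / √([pt(1−pt) + pc(1−pc)]/n)}, with Δ = 0.161 and p̄ = 0.2335.

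- At n = 550: (0.161 − 0.0500)/0.02505 = 4.43, so power is 0.999995.
- At n = 540: power is 0.999994.
- Joint bound: 1 − 0.05 − 0.05 = 0.90.

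The stated figures (more than 95% each, at least 90% jointly) are reproduced.

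**2. Gain from a severity stratum.** The documents give neither the severity mix nor response by severity. Assume 30% severe and a severity shift δ of 8 to 16 points in both arms. The prophylaxis stratum is ignored, because no rates by prophylaxis are given.

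- Unstratified: 0.314×0.686 + 0.153×0.847 = 0.3450. Divided by 550, SE = 0.02505.
- Variance removed over both arms: 2 × 0.30 × 0.70 × δ² = 0.42δ².

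| δ | 0.42δ² | Share of 0.3450 | SE falls by | 95% half-width, points |
|---|---|---|---|---|
| 0 | 0 | 0 | 0 | 4.91 |
| 8 points | 0.00269 | 0.8% | 0.4% | 4.89 |
| 16 points | 0.01075 | 3.1% | 1.6% | 4.83 |

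This equals roughly 9 to 35 extra subjects on 1,100: 1,100 × (0.3450/0.3423 − 1) and 1,100 × (0.3450/0.3342 − 1). A wider grid (50% to 80% moderate, odds ratio 1.5 to 4 for moderate against severe, margins held at 31.4% and 15.3%) gives 0.4% to 7.7% of variance, or 0.2% to 3.9% of SE. If the true effect were small enough for 90% power, removing 1% to 3% of variance would give 90.3% to 90.9%.

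**3. Why MBS type cannot be sized.** Taking the Phase 2b symptom rates (75 mg: photophobia 41.9%, phonophobia 52.3%, nausea 67.4%; placebo: 24.1%, 28.1%, 51.2%) as MBS stratum rates, with an assumed mix of 50/20/30, gives 5.6% of variance. These look like whole-arm rates:

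- The seven 75 mg percentages in Protocol 1.4.2 (31.4, 72.1, 67.4, 52.3, 41.9, 27.9, 69.8) are 27, 62, 58, 45, 36, 24 and 60 out of 86. No denominator from 20 to 259 fits except 86 and its multiples.
- The placebo percentages (15.3, 51.2 for both pain relief and nausea, 28.1, 24.1, 7.4, 42.4) are 31, 104, 57, 49, 15 and 86 out of 203. No other denominator in that range fits.

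If so, subjects without the symptom at onset count as free of it. With onset prevalence q, the rate among subjects who had the symptom is (r − (1 − q))/q. Two assumed sets of q, same 50/20/30 mix:

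| q (photo / phono / nausea) | 75 mg rates | Placebo rates | Variance removed |
|---|---|---|---|
| 95 / 85 / 60% | 38.8 / 43.9 / 45.7% | 20.1 / 15.4 / 18.7% | 0.3% |
| 85 / 75 / 80% | 31.6 / 36.4 / 59.3% | 10.7 / 4.1 / 39.0% | 8.9% |

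The documents do not say where in this range the truth lies.

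**4. Sensitivity analysis 6.** If a fraction f of each arm, all failures, falls outside the strata, both success rates and the risk difference are multiplied by 1/(1 − f): 1.02 at f = 2% and 1.05 at f = 5% (f assumed).

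**The case against.** The strongest reply is that stratifying by the randomization factor alone is standard and stated consistently in both documents, and that nothing turns on the change when power is above 99.9%. That is right on validity and on consequence. The size of the severity gain also rests wholly on assumed inputs. What remains is that a baseline value held for every mITT subject goes unused. Severity is recorded after randomization, but before dosing and under blinding, so it can serve as baseline.

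A reader might infer that leaving MBS type out of the primary MBS test is an oversight that gives up free precision. The documents do not support this. The removal is logged, the analysis is kept as a sensitivity analysis, and subjects with a missing or post-dose MBS have no valid stratum. The gain could be near zero.

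A reader might also infer that sensitivity analysis 6 discards failures. No exclusion is written: the text names the mITT population and is silent on where these subjects go.

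Finally, the present pooling rule is written for the two prophylaxis strata. It does not say which cells merge once a second factor is added, so it would have to be extended.

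**Conclusion.** This is a minor point of efficiency plus one gap in specification. Both co-primary analyses are valid as written. A severity stratum would remove about 0.8% to 3% of the variance for pain freedom under the assumed 30% severe and 8 to 16 point shift, which narrows the half-width by less than 0.1 percentage point (4.91 to 4.83 at most). No change in conclusion is expected at Phase 2b effects. The case for MBS type as a primary stratum is not made. The missing level in sensitivity analysis 6 does not depend on any of these assumptions and should be settled whatever is decided on severity.

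**What to change.** If the trial is still blinded:

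1. In SAP 5.7.3.1, add onset pain severity (moderate or severe) as a second stratum for pain freedom. State that cells with fewer than 5 subjects collapse over severity first. Show the prophylaxis-only result as a sensitivity analysis, and align Protocol 9.4.1.
2. Leave the primary MBS test in SAP 5.7.3.2 as it is.
3. In MBS sensitivity analysis 6, add a fourth level, no MBS reported before dosing, covering both missing and post-dose MBS. State a collapsing rule there too. While editing, reconcile the sentence in SAP 5.7.3.2 that makes reporting the MBS before taking study drug a failure with SAP Table 1 and SAP 5.7.2, which say the opposite.

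The cost is a few lines of text and no new data. The small downside is more strata. Timing must be checked first: version 2.0 of the SAP already describes post-hoc analyses. If unblinding has taken place, the primary analysis should not be altered, and a severity-stratified result could be shown only as post hoc.
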